7.2. GENERAL STATISTICAL PROCEDURES

Frequency distributions for categorical variables will be provided as number of subjects in the category and the percentages of the total number of subjects in the given population as noted. Counts of missing observations will be included in the denominator and presented as a separate category. Percentages will be reported to one decimal place.

A 2-sided 95% Wilson score CI for categorical variables without multiplicity adjustment will be provided where appropriate for efficacy analysis.

The descriptive statistics for continuous variables will be number of subjects, mean, standard deviation, median, minimum, and maximum. Mean and median will be reported to 1 more decimal place than the raw data, while the standard deviation will be reported to 2 more decimal places than the raw data. Minimum and maximum will be reported the same as the original data.

Summary tables may be replaced with listings when appropriate. For instance, an AE frequency table may be replaced with a listing if it only contains a few unique preferred terms (PTs) reported on relatively few subjects.

All listings (with the exception of All Subject listings) will be performed using the Safety Analysis Set and sorted by subject ID, ITT EAS, ITT PLT analysis set, and PP EAS membership (first subjects included in these sets) and, if applicable, by visit date unless otherwise specified.

The study drug name will be abbreviated in the tables, listings, and figures (TLFs) as “Bal” for balstilimab (AGEN2034).

Time intervals (in days), unless specified otherwise, will be calculated as difference between ending and start day + 1 day. For conversion to months, interval days will be divided by 30.4375.

7.3. SUBJECT ENROLLMENT

The number of subjects per region (USA, EU, other) and country in each analysis set will be summarized. In addition, a listing will be provided for All Subjects Analysis Set, including country, informed consent date, screening status (screen failure/enrolled), date of first dose, and analysis sets membership (Yes/No).

7.4. SUBJECTS DISPOSITION

Subject disposition will be summarized including

- Number of subjects treated
- Number of subjects dosed at least 12 months before data cutoff
- Median time and range (in months) from first dose until data cutoff
- Number of subjects who completed study treatment as per protocol
- Number of subjects with treatment ongoing at the time of analysis
- Number of subjects who discontinued treatment and primary reasons of discontinuation (with “Progression of disease (compared to baseline)” listed as “Progressive disease”).
- Number of subjects who completed the study as per protocol
- Number of subjects ongoing on study
- Number of subjects who discontinued study and primary reasons of discontinuation

7.5. DEMOGRAPHICS AND BASELINE CHARACTERISTICS

7.5.1. Demographic and Baseline Characteristics

Demographic and baseline characteristics will be tabulated using descriptive statistics. The following variables will be included:

- Age at screening (years)
- Age category (age < 55 vs age \geq 55, age < 65 vs age \geq 65, age < 75 vs age \geq 75)
- Race (since race was not reported for patients treated in France, these patients will be summarized under separate “Not reported (France)” category)
- Ethnicity
- Height (cm)
- Weight (kg)
- BMI (body mass index, kg/m²), defined as weight (kg) / height (m)²
- Eastern Cooperative Oncology Group (ECOG) performance status

Conversions for height and weight are as follows:

- Height (cm) = Height (inches) x 2.54
- Weight (kg) = Weight (lb) x 0.4536

Demographics and baseline characteristics will be listed in Safety Analysis Set.

7.5.2. Medical History

Medical history will be coded using the Medical Dictionary for Regulatory Activities (MedDRA) version 22.1 or higher.

Conditions and symptoms ongoing immediately prior to first dose will be summarized as “ongoing medical history at baseline”. Previous medical history data will be summarized separately as “medical history”.

The frequency count and percentage of subjects experiencing any medical conditions will be tabulated by system organ classifications (SOC) and PT. If a PT or SOC was reported more than once for a subject, the subject would only be counted once in the incidence for that PT or SOC.

7.5.3. Cancer History and Characteristics

Subjects’ cancer history prior to study entry will be summarized, including:

- Histological diagnosis at diagnosis classified as squamous, adenocarcinoma, adenosquamous, and other histology types.
- FIGO 2008 stage at diagnosis (In some cases FIGO data was not provided. To address this missing data point, for patients for whom AJCC-8 TNM staging was entered, but

FIGO is missing, TNM class will be mapped to FIGO using AJCC-8 algorithm described at the end of the section, both original and derived FIGO will be presented in listings).

- Time from original diagnosis to first dose date (years), calculated as (first dose date – initial diagnosis date)/365.25.
- PD-L1 tumor expression status in the most recent available pre-treatment biopsy (frequency and percentage of subjects classified as positive if combined positive score (CPS) $\geq 1\%$, and negative if CPS $< 1\%$).
- Tumor burden (sum of baseline target lesions by IERC assessment) using descriptive statistics and frequency ≤ 50 mm vs > 50 mm.

The mapping of AJCC-8 TNM stage to FIGO will be performed as prescribed by [American Joint Committee on Cancer](#):

Table 4: Mapping from AJCC-8 TNM to FIGO 2008 Stage

Stage 0	Tis	N0	M0
Stage I	T1	N0	M0
Stage IA	T1a	N0	M0
Stage IA1	T1a1	N0	M0
Stage IA2	T1a2	N0	M0
Stage IB	T1b	N0	M0
Stage IB1	T1b1	N0	M0
Stage IB2	T1b2	N0	M0
Stage II	T2	N0	M0
Stage IIA	T2a	N0	M0
Stage IIA1	T2a1	N0	M0
Stage IIA2	T2a2	N0	M0
Stage IIB	T2b	N0	M0
Stage III	T3	N0	M0
Stage IIIA	T3a	N0	M0
Stage IIIB	T1-T3	N1	M0
	T3b	Any N	M0
Stage IVA	T4	Any N	M0
Stage IVB	Any T	Any N	M1

Note: Any Nx, or Mx staging (that is, with unknown status in nearby lymph nodes or distant metastases) will be treated for the purpose of mapping as N0 or M0, respectively.

7.5.4. Prior Cancer Therapies and Procedures

Prior cancer systemic therapies will be summarized and listed including:

- Prior line of platinum-based systemic treatment in recurrent /persistent/metastatic setting as determined by Independent Review Committee
- Prior platinum-based treatment (string “plat” in reported or coded terms)

- Prior bevacizumab use (strings “bev” or “avastin” in reported or coded terms)
- BOR on the last treatment/therapy before enrollment
- Time from last day of last treatment to first dose date (months).

Listing will provide original term and PT coded using WHO Drug Sep 2019, the dates of start and end of therapy, location, intent, dose, BOR, and relapse date for each therapy recorded, as well as prior line of platinum-based systemic treatment in recurrent /persistent/metastatic setting as determined by Independent Review Committee.

Prior radiation therapies will be listed including the following information:

- Description
- Dose of radiation received
- BOR
- Time from last day of last treatment to first dose date (months).

Prior surgical procedures will be listed for Safety Analysis Set. Surgical procedures will be listed using both original entry as well as PT coded using WHO Drug Sep 2109.

7.5.5. Prior and Concomitant Medications

Prior and concomitant medications will be summarized and listed in Safety Analysis Set. Prior medication is defined as any non-study medication started before the first dose of balstilimab. Concomitant medication is defined as any non-study medication that was dosed on or after first study drug administration.

A prior medication could also be classified as “both prior and concomitant medication” if the end date is on or after first dose of balstilimab. In the listing, it will be indicated whether a medication is prior-only, concomitant-only, or both prior and concomitant medication.

7.6. SAFETY ANALYSIS

7.6.1. Drug Exposure

Balstilimab is administered intravenously (IV) every 2 weeks (Q2W).

Overall drug exposure will be summarized in Safety Analysis Set by the following parameters:

- Duration of treatment (week), calculated as: (last dose date – first dose date + 1)/7
- Number of balstilimab infusions received
- Total cumulative dose (mg), defined as the sum of the actual doses (mg) taken
- Dose compliance, defined as percentage of patients with any actual dose higher than 10%, 15%, or 20% or lower than 10%, 15%, or 20% relative to planned dose as entered on eCRF (Note: pharmacy manual specified that dose does not need to be adjusted for weight changes within 10%)

- Number of doses with infusion related reactions (as reported on drug administration eCRFs)
- Occurrences and number of actual doses exceeding adjusted planned dose by more than 5% (adjusting for up to 10 % weight loss.)

Per pharmacy manual, no adjustment in dose was required for body weight changes within 10%, therefore dose exceeding planned dose by $> 5\%$ will be interpreted as any dose 5% greater than the highest daily dose prescribed by the clinical trial protocol, after accounting for up to 10% changes due to decrease in body weight. Adjusted planned dose is calculated by multiplying prescribed dose level by adjusted weight W_{adj} . Denoting by W_0 and W the baseline and the most recent weights, adjusted weight is: $W_{adj} = W$ for $W \geq W_0$ and $W_{adj} = \min(W_0, 1.1 \times W)$ for $W < W_0$.

- Subjects with any dose interrupted/not completed
- Number of doses interrupted/not completed

Missing weight measurements in drug exposure analysis will be imputed by last observation carried forward, multiple measurements for the same timepoint will be averaged.

Details of study treatment exposure will be listed for Safety Analysis Set.

7.6.2. Adverse Events

Adverse events (AEs) will be coded using MedDRA v22.1 or later and will be classified by SOC and PT.

Severity of AEs will be assessed by investigators according to NCI-CTCAE v4.03, and AEs will be classified by the investigator as either related or not related to study drug

Pre-existing conditions are those that started before and continued after signing of informed consent. Prior AEs (non-treatment emergent) are those occurring after the subject signed the informed consent and before the administration of the first dose of study treatment. Immune-related AEs will be evaluated in the extended on-treatment period to account for late toxicities. A separate listing will be provided for AEs incurred after on-treatment period.

TEAEs are AEs with onset during or after administration of first dose, or the worsening of a pre-existing condition during the on-treatment period. Immune-related AEs will be considered TEAEs during the extended on-treatment period. In a sensitivity analysis, TEAEs will be defined as AEs with onset during or after administration of first dose, or the worsening of a pre-existing condition during the extended on-treatment period. A separate listing will be provided of all AEs with onset date, or worsening date between end of “On-treatment period” (35 days) and end of “Extended on-treatment period” (90 days).

Any missing onset date, causality, or severity must be queried for resolution. Unresolved / missing causality and severity will be handled according to the following rules:

- An unresolved causality will be considered treatment-related
- An unresolved severity will be identified as an unknown severity

AEs with partial dates will be considered TEAEs unless the AE can unequivocally be determined as not treatment emergent.

The following AEs are considered as AEs of special interest (AESIs):

- Infusion-related reactions per definition in NCI-CTCAE v4.03 specification (*per investigator assessment*)
- Lab-based hepatic toxicity: An elevated aspartate transaminase (AST) or alanine transaminase (ALT) lab value \geq to $3 \times$ upper limit of normal (ULN) with a corresponding elevated total bilirubin value $\geq 2 \times$ ULN, at the same time, an alkaline phosphatase lab value $< 2 \times$ ULN, as determined by way of protocol-specified laboratory testing or unscheduled laboratory testing
- Any AE suspected to be immune-mediated (i.e. an irAE) by the investigator

Unless otherwise stated, the number of subjects with an event (subject-wise) and the number of events (event-wise) will be provided for each summary.

Immune-related AEs will be tabulated using investigator-reported irAEs. .

Infusion related AEs will be tabulated using infusion-related reactions as reported by the investigators.

The following summaries by either SOC and PT or by PT and by toxicity grade will be provided. Summaries will be sorted by decreasing incidence of PT (within SOC, if applicable).

- TEAEs by SOC and PT, and by PT
- TEAEs by relationship to study drug, toxicity grade, SOC, and PT
- Drug-related TEAEs by SOC and PT, and by PT
- TEAEs leading to permanent treatment discontinuation by PT
- TEAEs leading to death by PT
- Drug-related TEAEs leading to permanent treatment discontinuation by PT
- Drug-related TEAEs leading to death by PT
- Serious TEAEs by SOC and PT, and by PT
- Serious TEAEs by relationship to study drug and toxicity grade, by SOC and PT
- Drug related serious TEAEs by SOC and PT, and by PT
- irAEs by SOC and PT, and by PT
- irAEs by relationship to study drug, toxicity grade, SOC, and PT
- Infusion-related TEAEs by SOC and PT, and by PT
- Infusion-related TEAEs by relationship to study drug, toxicity grade, SOC, and PT
- Laboratory abnormalities worsening (in at least one on-study measurement, relative to baseline) by NCI-CTCAE v4.03 criteria.
- ALT, AST, or bilirubin normal at baseline but with elevations $\geq 2 \times$ ULN.

The overall summary of will be reported by age (age < 55 vs age ≥ 55 , age < 65 vs age ≥ 65 , and age < 75 vs age ≥ 75), by race group including at least 5 subjects (groups < 5 subjects will be reported summarily as “Other”, patients treated in France who did not report race will be summarized as “Not reported (France)”), region (US vs EU vs other), and by normal vs abnormal creatinine and bilirubin levels at baseline.

In addition, the overall summary of AE incidence per month of drug exposure will be presented. Such a summary will report #patients/(total time of exposure in months) and #AEs/(total time of exposure in months.)

The analysis of irAEs in the above summaries will be performed using data as reported by investigator (the primary analysis). In addition, as an exploratory analysis, TEAEs using sponsor's broad and narrow definitions of irAEs, will be summarized. For each irAE, the summary will include median time (and range) to onset, median duration (and range) of the first instance of such AE per patient. Finally, descriptive statistics will be provided for time of onset, cycle of onset, and cumulative dose at onset of first irAE of any type.

If an SOC or PT was reported more than once for a subject, the subject would only be counted once in the incidence for that SOC or PT.

In tabulation by severity grade:

- For a given SOC, only the most severe SOC for each subject will be included
- For a given PT, only the most severe PT for each subject will be included

In addition, TEAEs (evaluated within extended treatment period) will be reported for the following clusters of immune-mediated AEs: pneumonitis, colitis and diarrhea, hepatitis, and liver function abnormalities, endocrinopathies, nephritis and renal dysfunction, skin disorders, other immune-related AEs. These clusters will be defined by the following MedDRA version 22.1 Preferred Terms:

- **Pneumonitis:** interstitial lung disease; pneumonitis; acute interstitial pneumonitis; immune-mediated pneumonitis
- **Colitis:** allergic colitis, autoimmune colitis, colitis, colitis erosive, colitis microscopic, enterocolitis hemorrhagic, eosinophilic colitis, necrotizing colitis, neutropenic colitis, enterocolitis, immune-mediated enterocolitis,
- **Diarrhea:** diarrhoea, diarrhoea hemorrhagic
- **Hepatitis:** acute hepatic failure, autoimmune hepatitis, hepatic failure, hepatitis, hepatitis acute, hepatotoxicity, liver injury, hepatocellular injury, immune-mediated hepatitis, immune-mediated hepatic disorder, drug-induced liver injury
- **Hypothyroidism:** autoimmune hypothyroidism, hypothyroid goiter, hypothyroidism, immune-mediated hypothyroidism, myxoedema, thyroid atrophy
- **Hyperthyroidism:** Basedow's disease, hyperthyroidism, Marine Lenhart syndrome, primary hyperthyroidism, immune-mediated hyperthyroidism, secondary hyperthyroidism, tertiary hyperthyroidism, thyroid dermatopathy, thyroid crisis, thyrotoxic periodic paralysis, toxic goiter, toxic nodular goiter,
- **Thyroiditis:** autoimmune thyroiditis, thyroiditis, thyroid acute, thyroiditis chronic, thyroiditis fibrous chronic, thyroiditis subacute, immune-mediated thyroiditis

- **Neuroendocrine Disorders (Pituitary-Adrenal insufficiency):** Addison's disease, adrenal androgen deficiency, adrenal insufficiency, adrenal suppression, adrenocortical insufficiency acute, glucocorticoid deficiency, hypoaldosteronism, mineralocorticoid deficiency, hypophysitis, lymphocytic hypophysitis, hypopituitarism
- **Diabetes** without prior history: type 1 diabetes mellitus, diabetes mellitus, latent autoimmune diabetes in adults, diabetic ketoacidosis.
- **Nephritis:** autoimmune nephritis, lupus nephritis, nephritis, nephritis hemorrhagic, immune-mediated nephritis
- **Rash:** pemphigoid, rash, rash erythematous, rash generalized, rash macular, rash maculopapular, rash pruritic, rash papular, immune-mediated dermatitis
- **Pruritus:** pruritus, pruritus allergic, pruritus generalized

Other Immune-related AEs: myocarditis, immune-mediated myocarditis, uveitis, immune-mediated uveitis, iritis, vitiligo, psoriasis, myositis, immune-mediated myositis, rheumatoid arthritis, systemic inflammatory response syndrome, sarcoidosis, autoimmune disorder, meningitis, encephalitis, encephalitis autoimmune, immune-mediated encephalitis, encephalopathy, autoimmune encephalopathy, immune-mediated encephalopathy, Guillain-Barre syndrome, myasthenia gravis, demyelination, stomatitis, pancreatitis, autoimmune pancreatitis, pancreatitis acute, immune-mediated pancreatitis, immune-mediated gastritis, lichen planus, colitis ulcerative, Crohn's disease, inflammatory bowel disease, hemolytic anemia, immune-thrombocytopenia, immune thrombocytopenic purpura, aplastic anemia, bacytopenia, pancytopenia, immune-mediated pancytopenia

For each cluster, the analysis will summarize: the total incidence and number of all TEAEs included in the cluster and by severity grade, % of pts who received treatment with pituitary and hypothalamic hormones and analogues, with corticosteroids for systemic use, or with thyroid therapy (concomitant medications in, respectively, H01, H02 and H03 ATC2 groups indicated for AE and started following AE onset but no later than the date of AE resolution or 21 days from AE onset, whichever comes earlier), % leading to dose hold, % leading to drug discontinuation, % resolved, time to onset of first TEAE and duration of all TEAEs and TEAEs of grade ≥ 3 .

The median duration of TEAE (in days) will be calculated using Kaplan Meier analysis for all patients and AE included in a cluster. Unresolved AEs or AEs with missing resolution information and date will be treated as censored data with the end of extended on-treatment period as censoring date.

Death summary table will present reasons for deaths on treatment period, in survival follow-up, and overall.

Death details will also be listed (if applicable) including:

- Number of doses of balstilimab
- Number of cycles

- Age at death
- Study days relative to first dose date, calculated as (death date – first dose date + 1)
- Number of days to death from last dose, calculated as (death date – last dose date + 1)
- Precipitating AE (if death is an outcome of AE)
- Immune-related AE (if death is an outcome of irAE per investigator)
- Cause of deaths

The following listings will be provided in Safety Analysis Set:

- All AEs (with TEAEs flagged)
- Related TEAEs
- Serious TEAEs
- TEAEs leading to treatment discontinuation
- TEAEs leading to death
- Death details (including age, study day, and days from last dose, AEs, and death cause).

Adverse events observed between signing the informed consent and first dose of study drug will be listed with negative study days.

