Schedule of Visits and Assessments	
Screening Period (Phase 1 and Phase 2) Screening assessments will be conducted within 42 days prior to first treatment dose, with associated evaluations and procedures.
 
Treatment Phase (Phase 1 and Phase 2) The treatment phase is divided into 2-week (Phases 1 and 2) or 3-week (Phase 1) cycles with associated evaluations and procedures that must be performed at specific time points. Each cycle begins with the administration of AGEN2034. Subjects will be treated for up to 24 months or until disease progression, unacceptable toxicity, or any criterion for stopping the study drug or withdrawal from the trial occurs. Tumor assessments will be conducted every 6 weeks from first dose until disease progression or a new line of therapy is initiated.
 
End-of-Treatment (Phase 1 and Phase 2)
 
Discontinuation Visit and Safety Follow-up Visit: All subjects who discontinue the trial treatment prematurely for an AE should have a full safety evaluation at the time of discontinuation (Discontinuation Visit).
 
A mandatory Safety Follow-up Visit should be scheduled 4 weeks after the last dose of study drug or before the initiation of a new antineoplastic treatment, whichever comes first. Subjects with an AE of Grade > 1 will be further followed until the resolution of the AE to Grade 0-1 or until beginning of a new antineoplastic therapy, whichever occurs first. Subjects with an adverse drug reaction (ADR) ongoing at the Safety Follow-up Visit must be followed up until the ADR resolves, becomes stable, or is considered not clinically significant by the Investigator.
 
Follow-up Phase (Phase 1 and Phase 2) Subjects who discontinue treatment will be followed for up to 12 months (Phase 1) or 24 months (Phase 2) after the last dose of study drug or until death, withdrawal of consent, or becoming lost to follow-up.
 
Follow-up Visits Visits with associated evaluations and procedures will occur every 3 months for up to 12 months following the last dose of study drug or until disease progression and/or start of a new line of therapy. Tumor assessments will continue every 6 weeks from first dose until discontinuation of study drug.
 
Survival Follow-up (Phase 2 only) Subjects in Phase 2 who present with progressive disease and/or start a new line of therapy will be contacted by phone every 2 months to assess for survival for up to 12 months after the last dose of study drug.

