### 7.2.1. Definition of the Adverse Event Reporting Period

The AE reporting period for safety surveillance begins when the subject provides written consent and continues until either 90 days after the last dose of study drug or the start of new anticancer treatment, whichever comes first. Following the End-of-Treatment Safety Follow-up Visit, only treatment-related AEs will be documented through the Treatment Follow-up Period of up to 12 months after the last dose of study drug or until disease progression and/or initiation of a new line of therapy, whichever comes first.

Any SAE suspected to be related to trial treatment must be reported whenever it occurs, irrespective of time elapsed since last dose of study drug.

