#### **8.3.4.1. Adverse Events**

Adverse events will be coded according to Medical Dictionary for Regulatory Activities (MedDRA) version 21.0. Severity of AEs will be graded using CTCAE (version 4.03) toxicity grading scale whenever possible.

Treatment-emergent AEs are AEs with onset dates during the on-treatment period, or the worsening of an event during the on-treatment period. Incidence of TEAEs, regardless of attribution, and AEs defined as related to AGEN2034 will be summarized by system organ class and preferred term, and described in terms of severity and relationship to AGEN2034.

Analysis of AES will be performed for events that are considered as treatment emergent. Adverse events leading to death or discontinuation of trial treatment, events with CTCAE Grade 3 or higher, study drug-related events, and SAEs will be summarized.

Indications of dose-related ADRs will also be examined.

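### The worsening limb of the SAP's TEAE definition covers only conditions that began before consent, so as written it leaves out a fully dated screening-onset AE that worsens on balstilimab under the same record

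*SAP*

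**What the plan says.** SAP 7.6.2 sorts events by when they begin.

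- Before consent: "Pre-existing conditions are those that started before and continued after signing of informed consent".
- Between consent and first dose: "Prior AEs (non-treatment emergent) are those occurring after the subject signed the informed consent and before the administration of the first dose of study treatment". The SAP makes no exception for a prior AE that later gets worse.
- TEAEs: "TEAEs are AEs with onset during or after administration of first dose, or the worsening of a pre-existing condition during the on-treatment period".

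The sensitivity definition widens the window to 90 days after the last dose but keeps the same limit on what may worsen: "the worsening of a pre-existing condition during the extended on-treatment period".

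Protocol 8.3.4.1 has no such limit: "Treatment-emergent AEs are AEs with onset dates during the on-treatment period, or the worsening of an event during the on-treatment period". Protocol section 8 allows the SAP to modify the planned analyses. SAP 4.1, which summarises the changes from the protocol, does not mention this one.

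**The concern.** The usual purpose of a worsening limb is to catch anything already present at first dose that deteriorates on drug. Here it is tied to consent instead, which leaves a gap between consent and first dose. An event that begins in that gap and rises from, say, Grade 1 to Grade 3 on balstilimab has no on-treatment onset and is not a pre-existing condition in the SAP's sense.

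The frequency, severity and duration of TEAEs are a Phase 2 secondary endpoint (Protocol 2.1.2, SAP 3.5). The TEAE flag also feeds the overall, drug-related and serious event tables in SAP 7.6.2, the tables of events leading to discontinuation or death, and the immune-mediated clusters. An event that fails the flag drops out of all of these. Because the 90-day sensitivity analysis carries the same limit, it cannot reveal the loss.

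**Working it through.** The plan gives no figure to reproduce, and no arithmetic settles the point. The check is to apply each definition to an event that worsens during treatment, according to when it began.

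**Can the affected class occur?** Yes. Protocol Synopsis: "Screening assessments will be conducted within 42 days prior to first treatment dose". Protocol 7.2.1: "The AE reporting period for safety surveillance begins when the subject provides written consent". Protocol 6.4.3.2.1 sends new clinically significant examination findings after consent to the AE record, not to medical history. Protocol 7.3 instead has AE recording start at first treatment, which conflicts with 7.2.1. The SAP follows 7.2.1, since it defines a prior-AE class and lists those events with negative study days.

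**Classification of a fully dated event that worsens during treatment, kept under one record:**

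| Onset | SAP class | TEAE, SAP main | TEAE, SAP sensitivity | TEAE, Protocol 8.3.4.1 |
|---|---|---|---|---|
| Before consent, continuing | Pre-existing condition | Yes | Yes | Yes |
| After consent, before first dose | Prior AE | **No** | **No** | Yes |
| At or after first dose | On-treatment onset | Yes | Yes | Yes, if within the protocol's on-treatment period |

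Only the middle row differs. Its onset window runs from consent to first dose, so up to 42 days.

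**Can *pre-existing* be read as *before first dose*?** Not on this text. The SAP defines the term by consent and gives the consent-to-dose events their own name. Elsewhere the SAP does use first dose as its reference: for baseline (5.1) and for ongoing medical history (7.5.2). That suggests a drafting slip rather than a decision.

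**Where does a row-two event appear?** In the listing of all AEs, without the TEAE flag, but in no TEAE summary.

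**The case against.** The best reply is that the wording gap may cost little in practice. Several parts of it stand.

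- **New record at worsening.** Protocol 7.2 has any unfavourable change in a subject's condition during the reporting period recorded as an AE, and 6.4.3.1 asks for assessment of new or worsening AEs. If a site opens a new record with an on-treatment onset, the event is a TEAE under the SAP's first limb. Neither section orders this explicitly, and 7.2 leaves the detail to eCRF conventions that are not among these documents. The route is plausible but not assured.
- **Partial dates.** SAP 5.6 sets an onset with a missing day, in the month of first dose, to the first dose date. SAP 7.6.2 treats partially dated events as TEAEs unless that is clearly wrong. Some screening events therefore become TEAEs, but because a date is missing, not because they worsened.
- **Other outputs.** Laboratory worsening is tabulated against baseline (SAP 7.6.2, 7.6.4), and deaths have their own summary. This covers part of the loss, but not symptomatic events in the related, serious or discontinuation tables. SAP 7.6.2 also counts immune-related AEs as TEAEs over the extended period; that lengthens their window but does not say that it overrides the prior-AE class.
- **A smaller class than 42 days suggests.** In Protocol Table 13, the clinical and laboratory screening assessments fall within 7 days of first dose, and clinically significant screening ECG findings go to medical history (6.4.3.4). That limits how many new events screening will detect.

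It is also true that the SAP may modify the protocol's plans and that the safety analysis is descriptive. Neither explains an unlisted change that takes on-drug worsening out of the tables.

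**Conclusion.** The point holds on the SAP's stated rule: a fully dated screening-onset AE that worsens on balstilimab under the same record is not a TEAE in the main or the sensitivity analysis, although Protocol 8.3.4.1 would count it. Within this limb the effect runs one way. The primary ORR analysis is untouched.

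Three stronger readings do not follow.

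- A reader might infer that such an event can never be a TEAE. The partial-date rules and the possible new record at worsening both contradict that.
- A reader might attach a percentage. If 10–30% of 150 subjects had a screening event and 10–30% of those worsened, the result would be 150 × 0.10 × 0.10 = 1.5 to 150 × 0.30 × 0.30 = 13.5 subjects (1–9%). Both rates are pure assumption, so this range should carry no weight. It would also count subjects who lose an event, not subjects who leave the any-TEAE count.
- A reader might infer that the SAP captures fewer TEAEs than the protocol overall. Its windows are wider: 35 days after last dose against 30, 90 days for immune-related events, and no cut at new anticancer therapy (SAP 5.3 and 5.4, Protocol 8.3.4). The narrowing concerns only which events may worsen into a TEAE.

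What remains is a misclassification of unknown, possibly small, size in a secondary safety endpoint. It should be corrected because the rule is wrong as stated and cheap to repair.

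**What to change.** In both TEAE sentences of SAP 7.6.2, replace the reference to a pre-existing condition with *any condition or AE with onset before the first dose*. Limit the label *Prior AEs (non-treatment emergent)* to those that do not worsen during the applicable on-treatment period: the standard one for the main analysis, the extended one for the sensitivity analysis. The worsening limb then agrees with Protocol 8.3.4.1. If the narrowing was intended, list and justify it in SAP 4.1 instead.

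The programming team should also confirm how the eCRF conventions record a rise in grade, because that decides how many events move. The derivation looks feasible: the SAP's listing of events between 35 and 90 days after last dose already relies on a worsening date.

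The cost is one phrase in two sentences, one qualified label and one derivation line. TEAE counts may rise slightly.
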